1. **Screening:** The Screening period is 45 days. Re-screening may be allowed upon discussion with the medical monitor. Central laboratory results should be used to confirm eligibility, however if repeat screening labs are required, local laboratory results can be used to confirm eligibility. The screening labs used to determine eligibility should be collected within 14 days prior to C1D1. In situations where laboratory results are outside of the permitted range, the investigator may opt to retest the subject and subsequent within range central lab screening results may be used to confirm eligibility. In case of multiple central laboratory data within the Screening period, the most recent data should be used to confirm eligibility. Subjects requiring transfusions to meet eligibility criteria are not eligible. Radiologic imaging used to confirm eligibility must be conducted within 28 days prior to C1D1.
2. All subjects will be treated for a maximum of 12 cycles or until the subject meets study treatment discontinuation criteria.
3. **Study Treatment Discontinuation Visit (End of Study Treatment):** The Study Treatment Discontinuation Visit will take place ≤ 7 days following the last dose or the decision by the investigator to discontinue study treatment.
4. **30-Day Safety Follow-up Visit:** A 30-Day Safety Follow-up Visit should occur 30 days (+7 days) after the last dose of ASP1650 and will include the assessments as shown in the Schedule of Assessments above.
5. Subject must have an available tumor specimen in a tissue block or unstained serial slides, or subject is an appropriate candidate for tumor biopsy and is amenable to undergoing a tumor biopsy during the screening period. If a biopsy is performed, collection from a site other than lymph nodes is preferred. A minimum of 1 FFPE tumor tissue block with adequate viable tumor cells (preferred) OR a minimum of 9 FFPE unstained slides are required. If ≥ 9 slides cannot be provided, the sponsor should be contacted for further guidance.
6. For subjects who signed an optional ICF, an optional on-treatment tumor specimen collected ± 7 days of the C4D1 visit may be provided. A minimum of 1 FFPE tumor tissue block with adequate viable tumor cells (preferred) OR a minimum of 9 FFPE unstained slides are required. In cases where a pretreatment biopsy was performed, collection of the on-treatment specimen from the same site is preferred.
7. Confirmation of Inclusion/Exclusion Criteria must be completed on C1D1. Clinical safety lab results from the screening visit will be used to determine eligibility. If repeat screening labs are required, local laboratory results can be used to confirm eligibility.
8. **Enrollment:** After confirmation of eligibility, the pharmacist/designee will contact the IRT system in order to enroll the subject. Enrollment may be performed up to 3 days prior to C1D1.
9. **ASP1650** will be administered as an intravenous infusion Q2W starting on C1D1. The 1000 mg/m² Q2W dose is administered as a 2-hour infusion and the 1250 mg/m² Q2W and 1500 mg/m² Q2W doses are administered as a 3-hour infusion. The infusion of ASP1650 should be completed in less than 6 hours from the start of infusion. Details of infusion preparation and storage requirements are defined in the pharmacy manual.
10. **Post-infusion Observation Period:** Following the first dose of ASP1650 on C1D1, the subject must be observed for 2 hours post ASP1650 infusion. If AEs are observed during this time, subsequent ASP1650 infusion times should be extended and subjects should continue to be observed for 2 hours post ASP1650 infusion. If the subject does not develop any AEs, the subject should be observed for 1-hour post-infusion for their subsequent ASP1650 infusions. The subject should be instructed to notify site personnel if they develop any AEs during this observation time period. In the event of grade 3 or 4 IRRs post ASP1650 infusion, samples for cytokine/chemokine should be collected. If any symptoms of potential anaphylaxis are observed, samples for tryptase should be collected.
11. **Glucose Finger Prick:** Due to the presence of the excipient trehalose (disaccharide) and dilution of ASP1650 with sterile 5% Dextrose Injection, a glucose check via finger prick at 1 hour post-infusion will be performed on Day 1 of all cycles. For diabetic subjects, additional glucose checks via finger prick should be performed as clinically indicated. If glucose check via finger prick is not available, glucose check via blood sampling is acceptable.

Footnotes continued on next page

12. Physical Exam: should include height (at Screening only), weight and ECOG performance status. All assessments should be taken predose on dosing days. A full physical exam is required at Screening. The physical exam only needs to be repeated on C1D1 if clinically significant changes from Screening are observed (in the opinion of the investigator). Targeted (symptom driven) physical exams should be conducted Q2W on day 1 of each cycle.
13. Vital signs (pulse, blood pressure, temperature) should be taken during every visit at the following time points:
 - Pre-dose at every visit
 - C1D1 and C2D1: Every 15 (\pm 5) minutes during ASP1650 infusion
 - Subsequent ASP1650 infusions: every 30 (\pm 10) minutes during ASP1650 infusions if the subject did not develop any AEs during the Post-infusion Observation Period of cycles 1 and 2. If subject develops AEs during C1D1, C2D1 or subsequent ASP1650 infusions, then collect every 15 (\pm 5) minutes during ASP1650 infusion
 - At 30 (\pm 10), 60 (\pm 10) and 120 (\pm 10) minutes post ASP1650 infusion during the Post-infusion Observation Period (for 1 or 2 hours; see footnote 10) 120 minute collection to be done only when observation period is 2 hours.
 - Unscheduled if clinically indicated
14. ECGs: a single ECG will be performed at Screening, the Study Treatment Discontinuation Visit, the 30-Day Follow-up Visit, and if clinically indicated or per local requirements. ECGs will be locally read. When collected on the same day, ECG should be collected prior to pharmacokinetic samples.
15. Imaging Assessments: Radiologic imaging will be evaluated at Screening (must be conducted within 28 days prior to C1D1) and every 6 weeks (+ 7 days) counting from C1D1 for the first 24 weeks and then every 12 weeks (\pm 7 days) thereafter until subject develops radiological disease progression per RECIST v1.1 by local investigator assessment or starts other systemic anticancer treatment, whichever comes earlier. Imaging will include CT scans with contrast of the thorax, abdomen, and pelvis. If CT scan with contrast is medically not feasible, MRI or CT scan without contrast may be used for imaging. Bone scans (or focal X-ray) or brain imaging should be performed if metastatic disease in bone or brain is suspected, respectively. The same mode of imaging should be utilized throughout the study unless medical necessity requires a change.
16. Laboratory Assessments: Laboratory tests must be sent to the central laboratory for analysis. Central laboratory results should be used to confirm eligibility, however if repeat screening labs are required, local laboratory results can be used to confirm eligibility. Laboratory tests will be reviewed by the investigator prior to any study treatment. In the event that the central laboratory results are not available in time for treatment decisions, local certified laboratory tests may be used. Holidays and weekends should be taken into account when scheduling these collections. Additional assessments may be done centrally or locally to monitor AEs or as clinically indicated. Clinical significance of out-of-range laboratory findings is to be determined and documented by the investigator/subinvestigator who is a qualified physician.
17. Thyroid Function Tests (TSH and T4): Thyroid function tests will be collected at C1D1 predose, at the Study Treatment Discontinuation Visit, and during the study treatment period if clinically indicated.
18. Coagulation (PT, PTT and INR): Coagulation tests should be done at Screening, during study treatment period if clinically indicated and at Study Treatment Discontinuation Visit. Central lab results must be used to confirm eligibility. Ongoing evaluation should be continued for subjects who are receiving therapeutic anticoagulation according to local standard of care.

Footnotes continued on next page

19. Exploratory Biomarker (Serum and Plasma) samples should be taken at predose on day 1 of cycles 1, 2 and every other cycle (C4, C6 etc.) and at the Study Treatment Discontinuation Visit
 - C1D1: Predose
 - C2D1: Predose
 - C4D1: Predose
 - C6D1: Predose
 - C8D1: Predose
 - C10D1: Predose
 - C12D1: Predose
 - ASP1650 Study Treatment Discontinuation Visit
20. Tumor Markers (AFP and β hCG) Samples for the measurement of serum AFP and serum β hCG to be collected predose at every treatment cycle and during the post treatment period every 6 weeks + 7 days for the first 24 weeks and then every 12 weeks \pm 7 days thereafter to align with imaging assessment until the subject develops radiological disease progression per RECIST v1.1 by local investigator evaluation or starts other systemic anticancer treatment.
21. Optional PGx: for subjects who signed a separate ICF, an optional whole blood sample for PGx for exploratory biomarker analysis may be collected prior to first study drug administration.
22. Optional Post-Progression Tumor Sample: for subjects who signed a separate ICF, an optional post-progression tumor sample for exploratory biomarker analysis may be collected following disease progression per RECIST v1.1 by local investigator and prior to initiation of subsequent anticancer therapy.
23. AEs: AEs and SAEs (regardless of causality) will be collected from the time of signed informed consent through 30 days following the last dose of study treatment or until initiation of a new anticancer treatment, whichever comes first.

Table 2 ASP1650 Pharmacokinetic and Immunogenicity Schedule

Study Day (1 Cycle = 14 Days)		Time (relative to dosing in each cycle)	Window	ASP1650 Pharmacokinetics Safety Lead-in Phase and all Subjects from Simon Stage I of Phase 2	ASP1650 Pharmacokinetics Simon Stage II of Phase 2	ASP1650 Immuno- genicity
Screening						
Cycles 1	Day 1	Predose (0 hr)	within 60 minutes prior to dosing	X	X	X
		1.5 hrs after start of infusion	± 15 minutes	X		
		Immediately after end of infusion	within 10 minutes after the end of the infusion	X	X	
		0.5 hr after end of infusion	± 5 minutes	X		
		1.5 hrs after end of infusion	± 15 minutes	X		
		3 hrs after end of infusion	± 15 minutes	X		
		6 hrs after end of infusion	± 30 minutes	X		
		24 hrs after end of infusion	± 120 minutes	X		
		48 hrs after end of infusion	± 120 minutes	X		
		72 hrs after end of infusion	± 120 minutes	X		
Cycle 2	Day 1	Predose (0 hr)	within 60 minutes prior to dosing	X	X	
Cycle 3	Day 1	Predose (0 hr)	within 60 minutes prior to dosing	X	X	
		1.5 hrs after start of infusion	± 15 minutes	X		
		Immediately after end of infusion	within 10 minutes after the end of the infusion	X	X	
		0.5 hr after end of infusion	± 5 minutes	X		
		1.5 hrs after end of infusion	± 15 minutes	X		
		3 hrs after end of infusion	± 15 minutes	X		
		6 hrs after end of infusion	± 30 minutes	X		
		24 hrs after end of infusion	± 120 minutes	X		
		48 hrs after end of infusion	± 120 minutes	X		
		72 hrs after end of infusion	± 120 minutes	X		
Cycle 4	Day 1	Predose (0 hr)	within 60 minutes prior to dosing	X	X	
Cycle 5	Day 1	Predose (0 hr)	within 60 minutes prior to dosing	X	X	X
Cycles 6 to 8	Day 1	Predose (0 hr)	within 60 minutes prior to dosing	X	X	
Cycle 9	Day 1	Predose (0 hr)	within 60 minutes prior to dosing	X	X	X
Cycles 10 to 12	Day 1	Predose (0 hr)	within 60 minutes prior to dosing	X	X	
Study Treatment Discontinuation Visit				X		X
30-day Safety Follow-up Visit				X		X

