Vital Signs ¹³	X	X		X	X
12-lead ECG ¹⁴	X	If clinically indicated and/or per local requirements		X	X

Table continued on next page

VISIT	Screening ¹	Study Treatment Period (Each Cycle = 14 Days)		Follow-up	
		Cycles 1 to 12²		Study Treatment Discontinuation Visit ³	30-Day Safety Follow-up Visit ⁴
Day		1	2 to 14	≤ 7 days from date of last dose or investigator decision to discontinue dose	30 days from date of last dose
Visit Window (business days)	-45 to -1	+5*	(no visit)	0	+7
Image Assessment ¹⁵	X	Every 6 weeks (+ 7 days) counting from C1D1 for the first 24 weeks, and then every 12 weeks (± 7 days) until subject develops radiographic disease by RECIST v1.1 or starts other systemic anticancer therapy			
Clinical Safety Labs ¹⁶	X	X		X	X
Thyroid Function Test (TSH, T4) ¹⁷		X	If clinically indicated	X	
Coagulation Parameters (PT, PTT and INR) ¹⁸	X	If clinically indicated		X	
Pharmacokinetics of ASP1650 (Serum)		See Table 2 below for sample collection schedule			
Antidrug Antibodies (ADA) for Immunogenicity		See Table 2 below for sample collection schedule			
Exploratory Biomarkers (Serum) ¹⁹		X		X	
Exploratory Biomarkers (Plasma) ¹⁹		X		X	
Tumor Markers (AFP, βhCG) ²⁰	X	X			
Whole Blood Sample for PGx (optional) ²¹		X			
Post-progression Tumor Sample (optional) ²²				X	
Concomitant Medication	X	X		X	X
AE²³	X	X		X	X

ADA: antidrug antibody; AE: adverse event; AFP: alpha-fetoprotein; βhCG: beta human chorionic gonadotropin; C: cycle; CT: computerized tomography; D: day; ECG: electrocardiogram; ECOG: European Cooperative Oncology Group; FFPE: formalin fixed paraffin embedded; ICF: informed consent form; INR: international normalized ratio; IRC: independent review committee; IRR: infusion-related reaction; IRT: interactive response technology; MRI: magnetic resonance imaging; PGx: pharmacogenomics; PT: prothrombin time; PTT: partial thromboplastin time; Q2W: every 2 weeks; RECIST: Response Evaluation Criteria In Solid Tumors; SAE: serious adverse event; T4: thyroxine; TSH: thyroid stimulating hormone

Footnotes continued on next page

*+5 day visit window does not apply to C1D1.

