Samples for pharmacokinetics, immunogenicity and biomarkers will be collected. An optional on treatment tumor tissue sample may be collected. Pharmacogenomics (PGx) and post-progression tumor samples may be collected for those subjects who sign separate informed consent forms (ICFs).

Follow-up Period

Following discontinuation from study treatment, subjects will have a Study Treatment Discontinuation Visit ≤ 7 days after their last dose of study drug or decision by the investigator to discontinue treatment, in addition to a Safety Follow-up visit at 30 days (+7 days) after their last dose of study drug.

If a subject discontinues study drug prior to radiologic progression, the subject should enter the Post-Treatment Follow-up Period. The subject should continue to undergo imaging assessments and serum AFP and serum βhCG every 6 weeks + 7 days counting from C1D1 for the first 24 weeks and then every 12 weeks ± 7 days thereafter until 1 of the following events occurs:

- Radiological disease progression
- Subject starts another anticancer treatment

All post-progression anti-cancer therapies including date and site of progression will be recorded on the electronic case report form (eCRF).

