5.3.1.2 Response Criteria Based on Modified RECIST v1.1

For subjects with measurable disease at baseline, the following criteria in [Table 4](#) will be used:

Table 4 Response Criteria Based on Modified RECIST v1.1

Serum Markers	Target Lesions	Non-Target Lesions	New Lesions	Overall Timepoint Response Assessment	
	(target lesion response)	(non-target lesion response)	(unequivocal new lesions)		
Values that fall below the ULN for the assay employed	CR	CR	No or Equivocal	CR	
	CR	Not Applicable	No or Equivocal	CR	
	Not applicable	CR	No or Equivocal	CR	
For both AFP and beta-hCG, no increase \geq 50% in 2 samples at least 1 week apart compared to nadir values, at least one of the values are above ULN	CR	CR	No or Equivocal	PR	
	CR	Not Applicable	No or Equivocal	PR	
	Not applicable	CR	No or Equivocal	PR	
For both AFP and beta-hCG, no increase \geq 50% in 2 samples at least 1 week apart compared to nadir values	CR	Non-CR/Non-PD	No or Equivocal	PR	
	CR	NE/ND	No or Equivocal	PR	
	PR	CR	} = not PD	No or Equivocal	PR
	PR	Non-CR/Non-PD		No or Equivocal	PR
	PR	NE/ND		No or Equivocal	PR
	PR	Not applicable		No or Equivocal	PR
For both AFP and beta-hCG, no increase \geq 50% in 2 samples at least 1 week apart compared to nadir values	SD	CR	} = not PD	No or Equivocal	SD
	SD	Non-CR/Non-PD		No or Equivocal	SD
	SD	NE/ND		No or Equivocal	SD
	SD	Not applicable		No or Equivocal	SD
Any	PD	Any	Any	PD	
Any	Any	PD	Any	PD	
Any	Any	Any	Yes or Unequivocal	PD	
Increase \geq 50% in serum tumor markers AFP or beta-hCG in 2 samples at least 1 week apart compared to nadir values	Any	Any	Any	PD	
NE/ND	NE/ND	Not PD	No or Equivocal	NE	

CR: complete response; ND: not done; NE: non-evaluable; PD: progressive disease; PR: partial response; SD: stable disease.

Confirmatory assessment for CR or PR should be done at least 4 weeks after the date of the CR or PR was first observed.

In subjects whose only evidence of disease is elevated serum tumor markers ($> 2 \times$ ULN AFP or $> 2 \times$ ULN β hCG) at baseline, the modified RECIST v1.1 will reduce to serum tumor marker response criteria described in Section 5.3.1.3. In subjects whose only evidence of disease is elevated serum tumor markers ($> 2 \times$ ULN AFP or $> 2 \times$ ULN β hCG) at baseline, confirmatory assessment for CR or PR is not required.

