6 DISCONTINUATION

6.1 Discontinuation of Individual Subject(s) From Study Treatment

The study treatment period is a maximum of 12 treatment cycles. A subject is free to withdraw from the study treatment and/or study for any reason and at any time without giving reason for doing so and without penalty or prejudice. The investigator is also free to terminate a subject's involvement in the study at any time if the subject's clinical condition warrants it.

The subject will be discontinued from study treatment if any of the following occur:

- Investigator determines it is in the subject's best interest to discontinue study treatment
- Subject develops disease progression based on serum tumor markers or radiological disease progression as assessed by the investigator.
 - If the investigator believes that the subject is continuing to derive clinical benefit (asymptomatic and/or without worsening of performance status or overall health) from study treatment, and an increase in tumor burden is not likely to affect vital organ function, the subject may remain on study treatment up to a maximum of 12 treatment cycles.
- Subject starts another systemic chemotherapy, immunotherapy, radiotherapy or other treatment intended for antitumor activity.
- Subject starts other investigational agent or device.
- Subject develops unacceptable toxicity.
- Subject has a delay of study treatment for ≥ 28 days from when the next study treatment was scheduled to be administered. However, restarting study treatment after dosing delay (beyond ≥ 28 days from when the next study treatment was scheduled to be administered) may be allowed based on investigator consultation with, and approval of, the Astellas medical monitor.
- Subject develops inter-current illness that the investigator determines may jeopardize the subject's safety if the subject continues to receive study treatment.
- Significant deviation from the protocol or eligibility criteria as determined by the sponsor.
- Subject declines further treatment.
- Subject is lost to follow-up despite reasonable efforts by the investigator to locate the subject.
- Subject is noncompliant with the protocol based on investigator or medical monitor assessment.

NOTE: If a subject discontinues ASP1650 prior to disease progression per modified RECIST v1.1 and is not receiving any other systemic anti-cancer therapy, the subject must continue to undergo radiological assessments per protocol-specified schedule.

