5.2.3 Progression-Free Survival (PFS)

PFS is defined as the time from the date of first dose until the date of disease progression as assessed by modified RECIST 1.1, or until death due to any cause. If a subject has neither progressed nor died, the subject will be censored at the date of last disease assessment or at the date of registration if no post-baseline radiological assessment is available. Subjects who receive any further anticancer therapy for the disease before disease progression will be censored at the date of the last disease assessment before the anticancer therapy started. If progression or death occurs after missing 2 scheduled disease assessments, the subject will be censored at the date of last disease assessment or at the date of registration if no post-baseline disease assessment is available. A subject has missed 2 scheduled disease assessments if the gap between two disease assessments is more than 2.5 times the scheduled disease assessment interval. During treatment, this will be 105 days (2.5 x 42 days during treatment for the first 24 weeks); during the follow-up period this will be 210 days (2.5 x 84 days during follow-up).

PFS (in days) is calculated as:

(Date of death, or Progression assessed by modified RECIST 1.1, or censoring) – (Date of first dose) +1.

To apply the cut-off date to PFS is to exclude disease assessments, death and anti-cancer therapy date after cut-off date in the analysis.

Note: Patient cannot be censored at “Not Evaluable (NE)”. If NE is the only previous assessment, then PFS will be censored at Day 1.

PFS will be calculated for each subject using RECIST 1.1 alone, and serum markers alone.

Table 3 PFS Definition

Situation	Date of Event or Censor	Outcome
No evaluable post-baseline efficacy assessments, no death	Date of first dose	Censor
Subject did not receive new anti-cancer therapy:		
Disease progression documented per modified RECIST v1.1	Date of PD	Event
No disease progression, but death recorded on eCRF	Date of death	Event
No PD nor death	Date of last efficacy assessment or at the date of first dose if no postbaseline efficacy assessment is available	Censor
Subject received new anti-cancer (ACT) therapy:		
Disease progression documented per modified RECIST v1.1 after new ACT	Date of last efficacy assessment before start of new anti-cancer therapy or at the date of first dose if no post-baseline efficacy assessment is available	Censor

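### AFP and βhCG are not scheduled at the discontinuation or 30-day visit, so a first marker rise at the last Day 1 waits 2 to 7 weeks for its second sample and can end as a censored PFS time

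*Protocol*

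**What the plan says.** **Marker draws.** In Protocol Table 1 the tumor-marker row is marked at Screening and at Day 1 of each cycle. The columns for the Study Treatment Discontinuation Visit and the 30-day Safety Follow-up Visit are blank. Both columns are marked for clinical safety labs. Footnote 20 has the samples "to be collected predose at every treatment cycle and during the post treatment period every 6 weeks + 7 days for the first 24 weeks", then every 12 weeks, "to align with imaging assessment until the subject develops radiological disease progression per RECIST v1.1 by local investigator evaluation or starts other systemic anticancer treatment". Protocol 2.2.1 covers subjects who stop drug before radiologic progression: "The subject should continue to undergo imaging assessments and serum AFP and serum βhCG every 6 weeks + 7 days counting from C1D1".

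**Marker progression.** The PD row of Protocol Table 4 (SAP Table 1) requires an increase of at least 50% "in serum tumor markers AFP or beta-hCG in 2 samples at least 1 week apart compared to nadir values". Protocol 5.3.1.3 has the same two-sample requirement for the marker-only criteria.

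**Visit timing.** Table 1, footnote 3: "The Study Treatment Discontinuation Visit will take place ≤ 7 days following the last dose or the decision by the investigator". Footnote 4 puts the 30-day visit 30 to 37 days after the last dose.

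**Stopping.** Protocol 6.1 lists "Subject develops disease progression based on serum tumor markers or radiological disease progression as assessed by the investigator" as a reason to stop. It separately lists the investigator's judgement of the subject's best interest.

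**PFS.** SAP 5.2.3 states: "Subjects who receive any further anticancer therapy for the disease before disease progression will be censored at the date of the last disease assessment" preceding that therapy. SAP Table 3 repeats the rule. The SAP also derives PFS by RECIST 1.1 alone and by serum markers alone.

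**The concern.** One rise is not an event; the second sample makes it one. A subject whose marker first rises at his last Day 1, and who then stops, passes through one or two study visits where blood is drawn but no marker is measured. The sample that could confirm progression waits for the imaging calendar. Sampling ends if he starts another systemic anticancer treatment before then, and the SAP censors him at his last assessment before that treatment.

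Censoring of this kind is likely to be related to the outcome, since a subject with a rising marker who moves to another treatment is plausibly progressing. Kaplan-Meier estimates treat such subjects as having the same prospects as those still followed, so PFS would tend to look longer. The exposed estimates are PFS by modified RECIST v1.1, a secondary endpoint, and the marker-only version. Marker-led progression is what the modified criteria add to RECIST v1.1. The SAP has no sensitivity analysis counting new therapy as a PFS event, so the effect would not show in the results.

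**Working it through.** **The plan's own figures.** The Simon rule (13 then 34 subjects, stop at 1 or fewer responses, reject at 6 or more) has P(reject | p) = Σ from x = 2 to 13 of Bin(x; 13, p) × P(Bin(21, p) ≥ 6 − x). This gives 0.0957 at p = 10% and 0.811 at p = 25%, in line with the stated 10% and 80%. PFS does not enter it. The SAP's missed-assessment limits also reproduce: 2.5 × 42 = 105 days and 2.5 × 84 = 210 days.

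**Step 1: the wait for the second sample.** Day 1 of cycle c falls 14(c − 1) days after C1D1. Imaging-aligned draws are due 42, 84, 126 and 168 days after C1D1, each +7. The wait is the next due draw minus 14(c − 1). This assumes no dosing delay and, for the last row, that the assessment due on that Day 1 was done that day.

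| Last dose, with first rise | Days from C1D1 | Next draw due | Wait | With window |
|---|---|---|---|---|
| C3, C6, C9, C12 | 28, 70, 112, 154 | 42, 84, 126, 168 | 14 | 14–21 |
| C2, C5, C8, C11 | 14, 56, 98, 140 | 42, 84, 126, 168 | 28 | 28–35 |
| C4, C7, C10 | 42, 84, 126 | 84, 126, 168 | 42 | 42–49 |

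Mean nominal wait: (4 × 14 + 4 × 28 + 3 × 42) / 11 = 294 / 11 = 26.7 days. Every wait meets the one-week spacing. The longest, 49 days, is below the 105-day limit, so that censoring rule is not triggered by the wait. A first rise seen at a post-treatment draw is a different case (nominal wait 42 days before week 24, 84 after) and is not counted here.

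**Step 2: when the event is lost.** All of these must hold: the first rise is at the last Day 1; the subject stops; no radiological PD is documented; there is no death without new therapy (SAP Table 3 counts that as an event); and new therapy, withdrawal or loss to follow-up precedes the second draw.

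**Step 3: what extra draws would do.**
- Discontinuation visit timed from the last dose: 0 to 7 days after the predose sample, so only day 7 meets the spacing.
- Discontinuation visit timed from a later decision: if the decision comes at the next planned Day 1 (day 14) and no dose is given, footnote 20 requires no predose sample, and the visit falls on days 14 to 21, which is valid.
- 30-day visit: replaces 42 by 30 for C4, C7 and C10 only. Mean (4 × 14 + 4 × 28 + 3 × 30) / 11 = 258 / 11 = 23.5 days.

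**Step 4: illustration only.** The documents do not say how soon new therapy starts. Assume an exponential time with median m days. The share starting before a draw at wait w is 1 − exp(−ln 2 × w / m), averaged over the 11 cycles. For m = 28: (4 × 0.293 + 4 × 0.500 + 3 × 0.646) / 11 = 46%.

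| Assumed m | As written | With 30-day draw | Valid draw on day 7 |
|---|---|---|---|
| 21 | 56% | 53% | 21% |
| 28 | 46% | 43% | 16% |
| 56 | 27% | 25% | 8% |
| 112 | 15% | 13% | 4% |

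These are shares of subjects in the Step 2 situation who would start new therapy before the draw. They do not allow for radiological PD or death, and are not estimates of PFS events lost.

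**The case against.** The strongest reply is that a second sample is already scheduled. Subjects who stop before radiologic progression keep having markers drawn on the imaging calendar, and for 4 of 11 cycles the nominal wait equals the 14-day on-treatment interval. A single rise does not meet the marker PD definition, so a subject who stays on drug is resampled at the next cycle. Protocol 5.8 allows extra blood for disease assessment, and footnote 16 allows further tests when clinically indicated. The population has no standard option or is ineligible for it (Protocol 3.1), so quick new therapy cannot be presumed. A rise may also have another cause; inclusion criterion 11 lists several. PFS is secondary and descriptive, and RECIST v1.1 PFS needs no marker confirmation.

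Most of this stands, and it rules out the stronger readings. A reader might infer that these subjects usually go without a second sample, or that confirmation becomes impossible. The schedule shows otherwise, and no rate is given for any step. A reader might also put a percentage on the inflation of median PFS; that needs the fraction of progressions lost, which the documents do not supply. Nor does the SAP's new-therapy rule govern duration of response: SAP Table 2 has no such row.

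The reply does not close the gap. Optional draws are not required ones, so ascertainment could differ between sites. Stopping on investigator judgement after one rise is allowed. For subjects whose only evidence of disease is elevated markers, Protocol 5.3.1.2 reduces modified RECIST to the marker criteria, so radiological PD may be no rescue. In marker-only PFS, the second sample is the only way to document progression.

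**Conclusion.** The point holds as a schedule gap with a conditional consequence. Marker confirmation after a rise at the last Day 1 can be delayed by up to 49 days in the first 24 weeks. If new therapy, withdrawal or loss to follow-up comes first, with no radiological PD and no death without new therapy, a possible marker progression becomes a censored time in PFS by modified RECIST v1.1. The same follows for marker-only PFS if Table 3's rules are applied to it. The likely direction of bias is upward; its size is unknown.

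Duration of response in confirmed responders can be affected similarly. Sampling stops at new therapy, and Table 2 censors responders without progression at their last efficacy assessment. That follows from the sampling rule, not from a new-therapy rule in the SAP.

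The primary ORR, the Simon cut-offs and the sample size do not change. The waits assume the nominal calendar; the percentages in Step 4 rest wholly on assumed medians. The case for acting is that the gap is avoidable at almost no cost, not that it has been shown to be large.

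**What to change.** In Protocol Table 1 and footnote 20, add AFP and βhCG to the Study Treatment Discontinuation Visit for subjects without radiological progression and before any new anticancer therapy. Where the last Day 1 sample showed a rise, time the draw at least 7 days after it and within the existing visit window: day 7 after the last dose, or within 7 days of a later decision to stop. Without that timing condition, a visit dated from the last dose would usually give a sample too early to count.

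Add the same draw at the 30-day visit under the same conditions. For a rise at the last Day 1 it is a modest backstop that mainly helps when the last dose is C4, C7 or C10.

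Cost: two extra serum assays at visits where blood is already drawn, plus the table and footnote wording.
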